- 8. A physician will see the subject prior to discharge to evaluate the subject's readiness for discharge.

Follow-Up Phone Call:

A follow-up phone call to the subject, (or caregiver/informant if applicable), will be conducted within 2 or 3 business days of the imaging day, but not before 48 hours post-injection, to confirm subject well-being and to collect information about any new adverse events. If both of these days are not business days, the follow-up phone call can occur the following business day. End of study for the purpose of adverse event reporting is defined as the completion of the follow-up phone call.

7.1.3. Death and Autopsy:

- 1. The responsible family member or caregiver/informant will be contacted immediately after the time of death to obtain a description of events leading up to death;
- 2. Subjects will not have an autopsy performed or be included in the primary analyses if death does not occur within nine months of the most recent imaging session or if tissue has not been acquired before the required number of autopsies for the study has been completed.
- 3. If subject and/or LAR consented, additional research and genetic testing will be performed on brain tissue.

Detailed autopsy procedures are described in the Technical Autopsy Manual.

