7.7.2. Adverse Event Definitions

Adverse Events

For reporting purposes, Avid will distinguish among pre-existing conditions, treatment emergent adverse events and trial-emergent adverse events. Pre-existing conditions (i.e., undesirable experiences, signs or symptoms that begin prior to the Screening Visit) will be recorded on the medical history and/or physical exam eCRF pages. Signs and symptoms that are believed to be due to the pre-existing condition (started prior to dose of investigational product) do not have to be recorded in the AEs section of the eCRF, unless there is an increase in frequency or severity. Additionally, signs or symptoms or changes in pre-existing conditions that occur outside the trial-defined adverse event reporting will be recorded in medical history.

An adverse event is any untoward medical occurrence associated with the use of a drug in humans, whether or not considered drug related. For the purposes of this study, untoward medical occurrences will be considered associated with the use of ¹⁸F-AV-1451, and thus be reported as treatment-emergent adverse events, if they occur within 48 hours after ¹⁸F-AV-1451 administration.

In the context of this study, adverse experiences including hospitalizations, medical complications and death are expected, since terminal illness is a requirement for entry into the study. Thus, if the investigator becomes aware of such events that occur after administration of the drug but outside the 48 hour reporting window, these will only be reported as adverse events if the investigator believes they are attributable to the investigational product or protocol procedure.

In order to capture possible adverse effects of trial participation, any untoward medical occurrences occurring after the informed consent until the administration of ¹⁸F-AV-1451 will be recorded in the CRF for reporting as trial-emergent adverse events. If the subject consents to a second ¹⁸F-AV-1451 PET scan, trial-emergent adverse events will be collected in a similar period, from either date of additional consent (if applicable) or the date the dose request for the second scan is submitted to Avid, up to the second administration of ¹⁸F-AV-1451.

Serious Adverse Event (SAE)

An SAE is an AE that results in one of the following outcomes or constitutes one of the following events:

- Death;

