7.7.4. Reporting of Serious Adverse Events

Study site personnel must alert Eli Lilly or its designee of any SAE within 24 hours of their awareness of the event via a sponsor-approved method. Alerts issued via telephone are to be immediately followed with official notification on study-specific SAE forms.

Serious adverse events occurring after a subject receives a dose of investigational product will be collected until 48 hours after the dosing of the investigational product, regardless of the investigator's opinion of causation. Therefore, SAEs that occur later than 48 hours after the dosing of the investigational product are not required to be reported unless the investigator feels the events were related to either investigational product or a protocol procedure.

If a subject experiences an SAE after signing informed consent(s), but prior to receiving investigational product, the event will be reported on the eCRF and to Eli Lilly or its designee. Previously planned (prior to signing the ICF) surgeries should not be reported

as SAEs unless the underlying medical condition has worsened during the course of the study.

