8.3. Safety Analysis

Safety vital signs measurements will be summarized by subject and by evaluation time point. Change from baseline (pre-dose time point) values will be determined and summarized.

Adverse events including injection site reactions will be summarized in terms of number and percentage of subjects experiencing an AE. The summary will be further broken down by system organ class (SOC) and preferred term using Medical Dictionary for Regulatory Activities (MedDRA) terms. Adverse events will also be presented by severity, relationship to treatment and seriousness. All subjects who experience SAEs or who discontinue due to AEs will be summarized.

Discontinuation

All subjects who discontinued participation prior to completing the study will be listed and their discontinuation reasons will be tabulated.

Vital Signs

Changes in vital signs from baseline will be summarized.

8.4. ¹⁸F-AV-1451 Image Analysis

¹⁸F-AV-1451 retention on PET images from subjects with valid autopsy data will be interpreted by visual examination as either

- Neocortical Uptake Not Consistent with an AD Pattern (AD-: no increased neocortical activity in any region or increased activity is isolated to the mesial temporal, anterolateral temporal or frontal region(s);
- Neocortical Uptake Consistent with an AD Pattern (AD+: increased neocortical tracer activity in the posterolateral temporal (PLT), parietal (including precuneus), or occipital region(s)); or
- Neocortical Uptake Consistent with an AD Pattern and with Likelihood of Disease Progression (AD++, which is a subset of AD+ (Neocortical uptake consistent with an AD pattern) where increased tracer activity is found in the parietal (including precuneus) region(s) regardless of uptake elsewhere, or in the frontal region in addition to PLT, occipital, or parietal region(s)).

For the purpose of testing the primary analyses, a scan interpretation will be considered positive (hypothesized to correspond to a B3 neuropathology score in Primary Analysis 1 and an NIA-AA score of high AD pathology in Primary Analysis 2) if the scan is interpreted as at least consistent with an AD pattern (AD+ or AD++). Details of the visual PET image review methods will be provided in the Blinded Read Manual.

Images will also be assessed quantitatively (semi-automated computerized measurement of SUVRs) for exploratory analysis purposes. Details of the analysis methods will be provided in the Quantitative Methodology Document.

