16.1. ADVERSE EVENTS

AEs will be coded to the SOC and PT using the MedDRA central coding dictionary, version 18.1.

TEAEs are defined as AEs that started or worsened in intensity or frequency on or after an ¹⁸F-AV-1451 injection and up to 48 hours after the ¹⁸F-AV-1451 injection. APPENDIX 1 describes the handling of partial dates and/or times for AEs. In case it is not possible to determine if an AE is treatment emergent or not, the AE will be classified by the worst case; i.e. treatment emergent.

An overall summary of number and percentage of subjects within each of the categories described in the sub-sections below will be provided.

Listings will include all AEs.

Document:	\\quintiles.net\enterprise\Apps\sasdata\SASa\sas\AVID\18F-AV-1451\Biostatistics\Documentation\SAP\Avid_18F-AV-1451-A16_SAP_Final_v1.0_20180815.docx		
Author:	XXXXXXXXXX	Version Number:	Final, v1.0
		Version Date:	15Aug2018
Template No:	CS_TP_BS016 – Revision 3	Reference:	CS_WI_BS005
Effective Date:	01May2012		

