16.1.1. ALL TEAEs

Incidence (frequencies and percentages) of TEAEs will be presented by SOC and PT, and also broken down further by maximum severity, relationship to study medication, and relationship to study procedures. In addition, incidence of TEAEs will be presented by PT only (i.e., not broken down by SOC). Subjects with multiple occurrences of a SOC/ PT will only be counted once for that SOC/PT in the tables. Summaries will be presented by alphabetical order of SOC and decreasing order of total frequency of PT.

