APPENDIX 2. PARTIAL DATE AND/OR TIME CONVENTIONS

ALGORITHM FOR PRIOR / CONCOMITANT MEDICATIONS

START DATE	STOP DATE	ACTION
Known/ Partial/ Missing	Known/ Ongoing	If stop date < ¹⁸ F-AV-1451 injection date, assign as prior If stop date ≥ ¹⁸ F-AV-1451 injection date or medication is ongoing, assign as concomitant.
	Partial	If known components of stop date show that: 
 • Stop date < ¹⁸F-AV-1451 injection date, assign as prior • Stop date ≥ ¹⁸F-AV-1451 injection date, assign as concomitant.
	Missing	Assign as concomitant

ALGORITHM FOR TREATMENT EMERGENCE OF ADVERSE EVENTS

START DATE/TIME	STOP DATE/TIME	ACTION
Known	Known, Partial, Missing	If start date/time < ¹⁸ F-AV-1451 injection date/time, then not TEAE If ¹⁸ F-AV-1451 injection date/time ≤ start date/time ≤ ¹⁸ F-AV-1451 injection date/time + 48 hours, then TEAE If start date/time > ¹⁸ F-AV-1451 injection date/time + 48 hours, then not TEAE
Partial, but known components show that it cannot be on or after ¹⁸ F-AV-1451 injection date/time and within 48 hours post-injection	Known, Partial, Missing	Not TEAE
Partial and known components show that it could be on or after ¹⁸ F-AV-1451 injection date/time and within 48 hours post-injection	Known, Partial, Missing	Assumed TEAE
Missing	Known	If stop date/time < ¹⁸ F-AV-1451 injection date/time, then not TEAE If stop date/time ≥ ¹⁸ F-AV-1451 injection date/time, then TEAE

Document: \\quintiles.net\enterprise\Apps\sasdata\SASa\sas\AVID\18F-AV-1451\Biostatistics\Documentation\SAP\Avid_18F-AV-1451-A16_SAP_Final_v1.0_20180815.docx

Author: XXXXXXXXXX

Version Number: Final, v1.0

Version Date: 15Aug2018

Reference: CS_WI_BS005

Template No: CS_TP_BS016 – Revision 3

Effective Date: 01May2012

Copyright © 2012 Quintiles Transnational Corp. All rights reserved.

The contents of this document are confidential and proprietary to Quintiles Transnational Corp. Unauthorized use, disclosure or reproduction is strictly prohibited.

START DATE/TIME	STOP DATE/TIME	ACTION
	Partial	If known components of stop date/time show that: 
 • Stop date/time < ¹⁸F-AV-1451 injection date/time, then not TEAE • Stop date/time ≥ ¹⁸F-AV-1451 injection date/time, then TEAE
	Missing	Assumed TEAE

Document: \\quintiles.net\enterprise\Apps\sasdata\SASa\sas\AVID\18F-AV-1451\Biostatistics\Documentation\SAP\Avid_18F-AV-1451-A16_SAP_Final_v1.0_20180815.docx

Author: XXXXXXXXXX Version Number: Final, v1.0
 Version Date: 15Aug2018

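### An adverse event attributed to the tracer or a procedure but dated more than 48 hours after injection enters none of the SAP's relatedness tables

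*SAP*

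**What the plan says.** **Collection.** Under Protocol 7.7.2, untoward events are linked to the tracer and will "thus be reported as treatment-emergent adverse events, if they occur within 48 hours" of administration. For events the investigator learns of outside that window, "these will only be reported as adverse events if the investigator believes they are attributable to the investigational product or protocol procedure". Protocol 7.7.4 applies the same filter to serious events: later ones "are not required to be reported unless the investigator feels the events were related to either investigational product or a protocol procedure". The follow-up call in Protocol 7.1.2, which asks about new adverse events and closes adverse event reporting, takes place "but not before 48 hours post-injection".

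**Classification.** SAP 16.1 states: "TEAEs are defined as AEs that started or worsened in intensity or frequency on or after an" injection, and it closes the window at 48 hours. For a known start later than that, SAP Appendix 2 reads "injection date/time + 48 hours, then not TEAE".

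**Tabulation.** SAP 16.1.1 presents TEAE incidence by SOC and PT, "broken down further by maximum severity, relationship to study medication, and relationship to study procedures". Protocol 8.3 is worded more widely: "Adverse events will also be presented by severity, relationship to treatment and seriousness".

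**The concern.** The collection rule and the tabulation rule pull in opposite directions. After 48 hours the protocol stops taking every event and keeps those with an attribution. The SAP then uses 48 hours as the only gateway to its relatedness tables, so the late events that were kept because someone judged them related are the ones left out.

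The usual reason for a short window in a terminally ill population is to keep out the expected events of the underlying illness. That reason has little force here, because the attribution filter already removes those events at collection.

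The result also sits oddly with the SAP's own cautious defaults. An event with no start date, no stop date and no recorded causality is counted as a related TEAE (SAP 16.1.1.2, 16.1.1.3 and Appendix 2). An event dated 49 hours after injection and positively attributed to the tracer is not.

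At stake is the related-AE incidence, a central safety statement for a diagnostic tracer. No efficacy analysis or success criterion is touched.

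**Working it through.** The plan gives no figure to reproduce, so the check applies the algorithm and then traces where each event lands.

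**1. Classification (SAP Appendix 2, known start).** With an injection at time T, an event is a TEAE if T ≤ start ≤ T + 48 h.

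- One injection at 0 h: starts at 0, 47.9 and 48 h are TEAEs. Starts at 48.1, 60, 72 and 120 h are not.
- Second injection assumed at 200 days (4,800 h): a start at 4,810 h (10 h after it) is a TEAE. A start at 4,849 h (49 h after it) is not.
- A partial start that cannot fall inside the window is not a TEAE.
- A partial start that could fall inside the window is a TEAE. So is a missing start, unless the stop date is before injection.

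Causality appears in no branch. The point therefore concerns events dated as starting after 48 hours.

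**2. Where a late attributed event can appear.**

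| Output | SAP section | Limited to TEAEs? | Late attributed event included? |
|---|---|---|---|
| SOC/PT incidence | 16.1.1 | Yes | No |
| Severity | 16.1.1.1 | Yes | No |
| Relationship to study medication | 16.1.1.2 | Yes | No |
| Relationship to study procedures | 16.1.1.3 | Yes | No |
| Injection site reactions | 16.1.2 | No | If it is one |
| Fatal AEs | 16.1.3 | No | If fatal |
| SAEs | 16.1.4 | No | If serious |
| Discontinuation | 16.1.5 | Yes | No |
| Listings | 16.1 | No | Yes |

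The injection site, fatal and SAE tables are by PT or by SOC and PT, not by relationship. So even a late attributed serious event enters no relatedness table. A late attributed event that is non-serious, non-fatal and not an injection site reaction is found only in listings.

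**3. Direction.** Adding related events to a count of subjects with a related event can raise it or leave it unchanged, never lower it. The omission therefore works one way.

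**4. Size.** The documents give no count of late attributed events. Assume k subjects whose only related event is late, and take the planned enrolment of about 200 as the number dosed:

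understatement = 100 × k / 200 percentage points

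- k = 0: 0
- k = 1: 100 × 1 / 200 = 0.5
- k = 2: 1.0
- k = 4: 2.0
- k = 6: 3.0

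A subject who already has a related TEAE adds nothing to the any-related-event line, although the late event may still be missing from its own PT row.

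**The case against.** **The SAP applies the protocol's own definition.** This stands. Protocol 7.7.2 sets the 48-hour treatment-emergent window. A reader might infer that the SAP misdefines TEAEs, and the documents do not support that. The gap comes from making TEAE status the only route into the relatedness tables.

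**Protocol 8.3 is short and generic, and 8.1 leaves detail to the SAP.** This stands in part. Section 8.3 does not mention events after 48 hours, but its wording is wider than TEAEs. A reader might go further and infer an undeclared change that SAP 3.5 should have listed. That cannot be established: SAP section 1 says the SAP is based on Amendment 3, and the available protocol is Amendment 2. The table shells mentioned in SAP section 8 are also unavailable.

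**Not everything late is attributed, and not everything late is lost.** This stands. Trial-emergent events before a second injection are collected whatever the attribution (Protocol 7.7.2). Protocol 10.7 asks for all adverse events to be documented whether or not drug-related, which sits awkwardly with 7.7.2. A reader might infer that every late event vanishes from the tables, but the SAE, fatal and injection site tables are not limited to TEAEs.

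**Several days of collection need not be involved.** This stands. A reader might infer that a Friday scan always pushes the call to Tuesday or Wednesday, 4 or 5 days out. The call window in Protocol 7.1.2 can also be read to allow Monday (day 3), about 1 day past 48 hours. After a Monday scan, a call on Wednesday or Thursday is 0 to 1 day past it. The wording fixes only that the call cannot come before 48 hours.

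**Late related events should be few.** This is plausible. The tracer mass is capped at 20 μg, 48 hours is about 26 half-lives of the isotope (2,880 / 109.77 = 26.2), and the 59 earlier subjects had only mild events, from which they recovered. It bears on the size, not on whether such events should be tabulated if they occur.

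**Conclusion.** The point holds as a gap in safety reporting. An adverse event dated as starting more than 48 hours after injection and attributed to the tracer or a procedure is in no relatedness table. Unless it is serious, fatal or an injection site reaction, it is in listings only. The effect on related-AE incidence runs downward only.

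Its size cannot be derived from the documents and may be nil. The figure of 0.5 percentage points per affected subject assumes about 200 dosed subjects and no other related event in that subject. A reader might infer that the safety result is materially understated, but nothing in the documents supports a particular size.

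The conclusion rests on the SAP text and on Protocol Amendment 2, and it assumes that neither Amendment 3 nor the table shells already provide for these events. The change is worth making because it is cheap and because the late events left out are those judged related.

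**What to change.** Leave the 48-hour TEAE definition in SAP 16.1 and Appendix 2 as it is. Add to SAP 16.1 a table of adverse events with onset more than 48 hours after the most recent injection that the investigator judged related to the tracer or a protocol procedure, serious and non-serious alike, by SOC/PT and severity. Count those subjects on a separate line of the overall related-AE summary.

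Widening the TEAE definition to take in late related events is not advised. It would contradict the window in Protocol 7.7.2 and mix two collection rules in one incidence: all causes up to 48 hours, attributed events only after that. The separate line avoids both problems.

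The cost is one more table, with no new data, and a related-AE incidence that may be slightly higher. If there were no such events, an empty table says so openly.

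### SAP Appendix 2 assumes an AE is treatment-emergent when its partial start date could fall in the 48-hour window, even if its stop date shows it ended before that injection

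*SAP*

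**What the plan says.** The treatment-emergence table in SAP Appendix 2 classifies an event first by how complete its start date/time is.

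- **Known start.** The start is compared with the injection and with injection plus 48 hours.
- **Partial start that is incompatible with the window.** The row begins "Partial, but known components show that it cannot be on or after" the injection. The result is not TEAE.
- **Partial start that is compatible with the window.** The row begins "Partial and known components show that it could be on or after" the injection. Known, partial and missing stop dates share one cell, and the single result is an assumed TEAE.
- **Missing start.** Here the stop date decides. A known stop before the injection gives not TEAE. A partial stop is tested in the same way ("If known components of stop date/time show that"). Only a missing stop gives an assumed TEAE outright.

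The definition is in SAP 16.1: "TEAEs are defined as AEs that started or worsened in intensity or frequency on or after an" injection, up to 48 hours after it. The same section limits the worst-case convention: "In case it is not possible to determine if an AE is treatment emergent or not, the AE will be classified by the worst case".

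Protocol 7.7.2 keeps a separate class of trial-emergent events, covering "any untoward medical occurrences occurring after the informed consent until the administration of" the tracer, with a similar collection period before a second scan.

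**The concern.** The compatible-partial-start row discards information that settles the question. If an event is known to have ended before an injection, it cannot have started or worsened after it. The table recognises this when nothing is known about the start, but not when the month or day of onset is known. More information about the event produces the wrong answer.

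Such records can arise. Pre-injection events are collected by design. Protocol 7.1.1 prefers screening within 45 days before imaging and lets some assessments take place on the imaging day, so a pre-injection event can share a calendar month or day with the injection. Protocol 7.7 asks for start and stop dates and times, while 7.7.3 mentions dates only, so a missing clock time on the injection day is plausible.

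What is at stake is the content of the TEAE tables in SAP 16.1.1 (by system organ class and preferred term, maximum severity, and relationship to tracer and to procedures). An event that the protocol would report as trial-emergent would appear there as treatment-emergent.

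**Working it through.** The plan gives no figure to reproduce. The check traces the decision table on constructed records.

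**Whose known components?** The phrase in the disputed row sits in the start date/time column. Where the table tests the stop date it says so separately ("If known components of stop date/time show that"). The row therefore cannot be read as already including a stop-date test.

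**Rules as written.** Let I be the injection time, S_lo and S_hi the earliest and latest start consistent with the recorded components, and E_hi the latest stop consistent with the recorded components.

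- Partial start: assumed TEAE if S_lo ≤ I + 48 h and S_hi ≥ I; otherwise not TEAE. E_hi does not enter.
- Missing start, with a known or partial stop: not TEAE if E_hi < I; otherwise TEAE.

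**Why the stop date is decisive.** A start cannot be later than its stop. If E_hi < I, the start is before I and nothing remains to worsen at or after I. The SAP 16.1 definition then fails with certainty, so the worst-case condition is not met.

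**Test records.** Take a hypothetical injection at 2017-05-20 10:00, so I + 48 h = 2017-05-22 10:00. For the first record, S_lo = 1 May and S_hi = 31 May. Since 1 May ≤ 22 May 10:00 and 31 May ≥ 20 May 10:00, the table returns an assumed TEAE, although E_hi = 12 May is before 20 May.

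| Start | Stop | Table as written | With stop-date check |
|---|---|---|---|
| 2017-05, day unknown | 12 May | assumed TEAE | not TEAE |
| 2017, month unknown | 12 May | assumed TEAE | not TEAE |
| 20 May, time unknown | 20 May 09:00 | assumed TEAE | not TEAE |
| 2017-04, day unknown | 12 May | not TEAE | not TEAE |
| missing | 12 May | not TEAE | not TEAE |
| 10 May, known | 12 May | not TEAE | not TEAE |
| 2017-05, day unknown | 21 May | assumed TEAE | assumed TEAE |

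Three of the seven records change, all of them events that ended before the injection. The last record is truly indeterminate and correctly stays an assumed TEAE. Rows one and five show the contradiction: the stop is identical, but the event is counted when its start month is known and excluded when nothing is known about its start.

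**Comparison within the same appendix.** The medication algorithm groups all start dates together ("Known/ Partial/ Missing") and classifies by the stop date, so a stop before injection means prior. The partial-start AE row is the exception.

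**The case against.** The strongest reply is that the main text already gives the right answer. SAP 16.1 defines a TEAE by onset or worsening at or after an injection, and Protocol 7.7.2 assigns pre-injection events to the trial-emergent class. Appendix 2 would then be only an incomplete convention beneath a clear definition. That is fair about intent, but it does not cure the table. No order of precedence is stated, and Appendix 2 is the explicit algorithm a programmer would implement.

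The points about reach and consequence do stand.

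- Several conditions must coincide: onset after the screening period begins, resolution before the injection, a partial start compatible with the window, and a stop recorded well enough to precede the injection. Sites must record dates, and Protocol 10.6 has a monitor verify eCRF data against source. The documents do not show that any such record exists.
- The error overcounts, which is the conservative direction. There is no comparator arm, SAP 7.4 plans no testing of safety outcomes, and all AEs are listed, so the dates of a misassigned event would be visible.

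A reader might also infer more than the documents support.

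- *Every partial start date is affected.* It is not; partial starts that cannot fall in the window are already not TEAE.
- *Every such event ended before any tracer was given.* This holds only for the first injection. An event that ended before a second scan may follow the first.
- *Misclassified events become tracer-related.* SAP 16.1.1.2 imputes that only if the relationship is also missing, and investigators are required to report it.
- *A low expected TEAE count would be materially inflated.* Neither document gives an expected count.

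**Conclusion.** The row is wrong as written. It contradicts the missing-start row of the same table and exceeds the limit that SAP 16.1 places on the worst-case rule. The conclusion is confined to events whose partial start is compatible with the 48-hour window and whose stop date/time, or its known components, precedes the injection in question.

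The consequence is a conservative overcount of TEAEs in descriptive safety tables. The number of records cannot be derived from the documents and is probably small. No primary, secondary or exploratory efficacy result is affected. The finding rests on a literal reading of the table and on the absence of any precedence rule; the test dates are hypothetical and carry no information about frequency. It is worth correcting because the rule misreports events whose status is certain, not because a material change in the safety profile has been shown.

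**What to change.** In SAP Appendix 2, split the compatible-partial-start row by stop date, following the row for a missing start:

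- if the stop date/time, or its known components, shows that the event ended before the relevant injection, the event is not a TEAE for that injection;
- otherwise, including when the stop is missing or its known components leave the matter open, it is an assumed TEAE.

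State that the rule is applied separately to each injection and that an event is a TEAE if it qualifies for any of them. The table does not at present say which injection applies to a subject with two scans.

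The cost is one divided row in the SAP and one extra condition in the derivation program. No further data are needed, and indeterminate events keep their worst-case classification.
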